8.4 Premature End-of-Treatment visit (Visit 9)

All subjects who prematurely discontinue study treatment must have Visit 9 performed as soon as possible but not longer than 7 days after the last dose of study treatment, provided that the subject's consent for this limited participation in the study has not been withdrawn.

Essential hypertension Protocol AC-080A201 Version 3 30 May 2016, page 74/112

Confidential

The following assessments are to be performed at premature EOT / Visit 9:

- Sitting BP and HR, and standing BP, measured by OBPM device.
- Physical examination and body weight.
- *12-lead ECG.
- *Laboratory test (i.e., hematology, blood chemistry, and pregnancy test if applicable).
- *Urinalysis (dipstick by site / UACR by central laboratory).
- Reporting of AEs and SAEs.
- Recording of changes in concomitant medications.
- *Assessment of childbearing potential and recording of changes in contraception methods.
- Check compliance with study treatment.
- Retrieve study treatment bottles.
- Make an appointment for the follow-up telephone call or, *for women of childbearing potential, an appointment for the follow-up visit.
- * If subject discontinued study treatment during run-in period,
- This test may not be performed, and
- For women of childbearing potential, a follow-up telephone call can be made instead of the follow-up visit.

8.5 Follow-up period

A follow-up telephone call must be performed 30 days after the last dose of the DB treatment and the following must be checked with the subject:

- Any changes in concomitant medication.
- Any AEs and SAEs.

For women of childbearing potential:

A visit must be scheduled 30 days after the last dose of the DB treatment instead of telephone call to perform a serum pregnancy test, in addition to the above mentioned assessments.

8.6 Unscheduled visits

Unscheduled visits may be performed at any time during the study. Depending on the reason for the unscheduled visit (e.g., loss of efficacy, AE, etc.), appropriate assessments [as specified in Table 1] may be performed based on the judgment of the investigator and must be recorded in the eCRF. After an unscheduled visit, the regular scheduled study visits must continue according to the planned visit and assessment schedule.

Essential hypertension Protocol AC-080A201 Version 3 30 May 2016, page 75/112

Confidential

9 STUDY COMPLETION AND POST-STUDY TREATMENT / MEDICAL CARE

9.1 Study completion

End-of-Study for a single subject is defined as the date of the 30-day follow-up telephone call / visit.

If a subject withdraws consent and does not wish to participate in further visits, the date of consent withdrawal is the EOS for this subject. If a subject is declared lost to follow-up [see also Section 9.2], the date of last contact is the EOS for this subject.

The overall study is considered completed when all subjects have completed their 30-day safety follow-up telephone call/visit.

Enrollment and screening failure rates will be monitored in order to limit the inclusion of subjects in excess of the planned number of randomized subjects. If some subjects are still in the run-in period when the planned number of randomized subjects is reached they will be allowed to continue until the Randomization visit (Visit 4) and beyond if they fulfill the randomization criteria.

9.2 Premature withdrawal from study

Subjects may voluntarily withdraw from the study for any reason at any time. Subjects are considered withdrawn if they state an intention to withdraw further participation in all components of the study (i.e., withdrawal of consent), die, or are lost to follow-up. If a subject withdraws consent, no further data will be collected in the eCRF from the date of withdrawal onward. The investigator may withdraw a subject from the study (without regard to the subject's consent) if, on balance, he/she believes that continued participation in the study would be contrary to the best interests of the subject. Withdrawal from the study may also result from a decision by Actelion for any reason, including premature termination or suspension of the study [see Section 9.3].

Subjects are considered as lost to follow-up if all reasonable attempts by the investigator to communicate with the individual fail. The site must take preventive measures to avoid a subject being lost to follow-up (e.g., document different ways of contact such as telephone number, home address, email address, person to be contacted in case the subject cannot be reached). If the subject cannot be reached, the site must make a reasonable effort to contact the subject, document all attempts, and enter the loss of follow-up information into the eCRF. The following methods must be used: at least three telephone calls must be placed to the last available telephone number and one registered letter must be sent by post to the last available home address. Additional methods may be acceptable if they are compliant with local rules/regulations (e.g., site staff visit to the subject's home), respecting the subject's right to privacy. If the subject is still

Essential hypertension Protocol AC-080A201 Version 3 30 May 2016, page 76/112

Confidential

unreachable after all contact attempts listed above, he/she will be considered to be lost to follow-up.

If premature withdrawal occurs for any reason, the reason for premature withdrawal from the study, along with who made the decision (subject, investigator, or Actelion) must be recorded in the eCRF.

If for whatever reason (except death or loss-to-follow-up) a subject was withdrawn from the study, the investigator should make efforts to schedule a last appointment/phone call to assess the safety and well-being of the subject, collect unused study treatment and discuss follow-up medical care. Data obtained during this last appointment/phone call will be recorded in the subjects' medical records but it will not be collected in the eCRF. The investigator must provide follow-up medical care for all subjects who are prematurely withdrawn from the study, or must refer them for appropriate ongoing care, as described in Section 9.4.

9.3 Premature termination or suspension of the study

Actelion reserves the right to terminate the study at any time globally or locally. Investigators can terminate the participation of their site in the study at any time.

If a study is prematurely suspended or terminated, Actelion will promptly inform the investigators, the IRBs/IECs, and health authorities, as appropriate, and provide the reasons for the suspension or termination.

If the study is suspended or prematurely terminated for any reason, the investigator in agreement with Actelion must promptly inform all enrolled subjects, and ensure their appropriate treatment and follow-up, as described in Section 9.4. Actelion may inform the investigator of additional procedures to be followed in order to ensure that adequate consideration is given to the protection of the subjects' interests.

In addition, if the investigator suspends or terminates a study without prior agreement from Actelion, the investigator must promptly inform Actelion and the IRB/IEC, and provide both with a detailed written explanation of the termination or suspension.

If the IRB/IEC suspends or terminates its approval / favorable opinion of a study, the investigator must promptly notify Actelion and provide a detailed written explanation of the termination or suspension.

9.4 Medical care of subjects after study completion / withdrawal from study

After the subject's study completion or premature withdrawal from the study, whichever applies, the investigator/delegate will explain to subjects what treatment(s)/medical care is necessary and available according to local regulations. Such care may include the use of drugs which were forbidden during the study. Female subjects of childbearing

Essential hypertension Protocol AC-080A201 Version 3 30 May 2016, page 77/112

Confidential

potential will be reminded of the need to maintain reliable contraception method for one month after study treatment stop and to perform a pregnancy test one month after study treatment termination.

10 SAFETY DEFINITIONS AND REPORTING REQUIREMENTS

10.1 Adverse events

10.1.1 Definitions of adverse events

An AE is any adverse change, i.e., any unfavorable and unintended sign, including an abnormal laboratory finding, symptom, or disease that occurs in a subject during the course of the study (i.e., from signing of the informed consent), whether or not considered by the investigator as related to study treatment.

A treatment-emergent AE is any AE temporally associated with the use of study treatment (from study treatment initiation in run-in period until 30 days after study treatment discontinuation) whether or not considered by the investigator as related to study treatment.

Adverse events include:

- Exacerbation of a pre-existing disease.
- Increase in frequency or intensity of a pre-existing episodic disease or medical condition.
- Disease or medical condition detected or diagnosed during the course of the study even though it may have been present prior to the start of the study.
- Continuous persistent disease or symptoms present at study start that worsen following the start of the study (i.e., signing of informed consent).
- Abnormal assessments, e.g., change on physical examination, ECG findings, if they
 represent a clinically significant finding that was not present at study start or
 worsened during the course of the study.
- Laboratory test abnormalities if they represent a clinically significant finding, symptomatic or not, which was not present at study start or worsened during the course of the study or led to dose reduction, interruption or permanent discontinuation of study treatment.

Overdose, misuse, and abuse of the study treatment should be reported as an AE and, in addition, study treatment errors must be documented in the study drug accountability log of the eCRF.

Essential hypertension Protocol AC-080A201 Version 3 30 May 2016, page 78/112

Confidential

10.1.2 Intensity of adverse events

The intensity of clinical AEs is graded on a three-point scale – mild, moderate, severe – and is reported on specific AE pages of the eCRF.

If the intensity of an AE worsens during study treatment administration, only the worst intensity should be reported on the AE page. If the AE lessens in intensity, no change in the intensity reporting is required.

If the intensity of an AE with an onset date between informed consent signature and start of study treatment and which is ongoing at the start of treatment worsens after the start of study treatment, a new AE must be completed in the eCRF. The onset date of this new AE corresponds to the date of worsening in intensity.

The three categories of intensity are defined as follows:

■ Mild

The event may be noticeable to the subject. It does not influence daily activities, and usually does not require intervention.

■ Moderate

The event may make the subject uncomfortable. Performance of daily activities may be influenced, and intervention may be needed.

□ Severe

The event may cause noticeable discomfort, and usually interferes with daily activities. The subject may not be able to continue in the study, and treatment or intervention is usually needed.

A mild, moderate, or severe AE may or may not be serious [see Section 10.3.1]. These terms are used to describe the intensity of a specific event. Medical judgment should be used on a case-by-case basis.

Seriousness, rather than severity assessment, determines the regulatory reporting obligations.

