10.1.5 Reporting of adverse events

All AEs occurring after study start (i.e., signing of informed consent) and up to 30 days after DB study treatment discontinuation must be recorded on specific AE pages of the eCRF.

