5.6.1.1 Treatment-emergent adverse events

Double-blind treatment-emergent AEs are defined as those AEs with onset on or after the double-blind treatment start date [see definition in Section 11.2] up to the double-blind treatment end date [see definition in Section 11.4] plus 30 days (included). Run-in treatment-emergent AEs are AEs with onset dates between the start and end dates of the run-in placebo (or the start of double-blind treatment, if applicable; limits included).

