11.2 Run-in treatment start date/time

The run-in treatment start date is the first day of intake of study treatment during the run-in period. It is derived from the first treatment start date (in chronological order) in the **Study Drug Log** eCRF where the 'Study Period' is 'SB RUN-IN'. If the start time of the run-in period is missing, it will be set to 00:00.

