11.4 Randomization date/time

The randomization date/time is taken from IVRS.

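### An adverse event that begins on run-in placebo and worsens on double-blind treatment probably keeps its run-in onset date, so the onset-only SAP rule leaves the worsening out of the by-arm AE tables

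*Protocol*

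**What the plan says.** **Recording.** Protocol 10.1.2 has two rules.

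- The general rule is "If the intensity of an AE worsens during study treatment administration, only the worst intensity should be reported on the AE page".
- The exception opens "If the intensity of an AE with an onset date between informed consent signature and start of study treatment". If such an event is still present when treatment starts and then gets worse, the site completes a new AE: "The onset date of this new AE corresponds to the date of worsening in intensity".

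**When study treatment starts.** Protocol 10.1.1 defines treatment-emergence as running "from study treatment initiation in run-in period until 30 days after study treatment discontinuation". SAP 11.2 uses the term the same way: "The run-in treatment start date is the first day of intake of study treatment during the run-in period". Where protocol Section 10 means the double-blind phase it usually says so, as in 10.1.5: "up to 30 days after DB study treatment discontinuation must be recorded on specific AE pages of the eCRF".

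**Counting.** SAP 5.6.1.1 states "Double-blind treatment-emergent AEs are defined as those AEs with onset on or after the double-blind treatment start date", with an end 30 days after the last double-blind dose. Run-in events are those with onset during run-in placebo. SAP 5.6.3 applies the same onset rule to SAEs. Neither section mentions worsening.

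**Display.** The AE tables by treatment group in SAP 13.9.1 and 13.9.4 are restricted to double-blind treatment-emergent events. Run-in tables use the Run-in Set, for which SAP 10.2 provides a total column only.

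**The concern.** Safety and tolerability of four doses is a secondary objective (protocol 2.2), and the trial is meant to find the dose or doses with the best balance of efficacy and tolerability for Phase 3 (protocol 1.3). The by-arm AE tables are a main source for that judgment. If an event already present on run-in placebo becomes worse on active drug and the tables cannot show it, part of the tolerability information is missing where doses are compared.

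Overlap between run-in and drug events is foreseeable. Protocol 1.2.1 reports that headache rose with dose in Phase 1 and was absent on placebo. Protocol 7.2.2 lists headache and dizziness among symptoms of hypertension or orthostatic hypotension. Protocol 10.1.4 anticipates exacerbation of the underlying disease when previous treatment is washed out.

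**Working it through.** The plan states no figure on this point, so the check traces one case through the rules: mild onset on run-in placebo, still ongoing at the first double-blind dose, severe during double-blind treatment.

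1. **Which recording rule applies?** The exception needs onset between consent and the start of study treatment. Protocol 8.1.1 has the first placebo dose taken at site at Visit 1, which lasts up to 72 h. The exception therefore covers at most 3 days. The run-in lasts 4 to 6 weeks, that is 28 to 42 days. Onset in those weeks falls under the general rule: one record, run-in onset date, worst intensity.
2. **Is it a double-blind treatment-emergent AE?** Onset precedes double-blind start, so under SAP 5.6.1.1 it is not. It is absent from the by-arm tables by organ class and preferred term, of related events and by maximum intensity (SAP 13.9.1).
3. **Where is it counted?** As a run-in treatment-emergent AE, in tables without dose columns. Its record now carries an intensity reached on double-blind treatment. The effect on run-in severity is small: the maximum-intensity table covers the Safety Set only, so at most a row of the run-in overview could change.
4. **What if it stops double-blind drug?** SAP 5.6.4 defines AEs leading to discontinuation by the action taken, with no onset limit. The by-arm tables in SAP 13.9.4 nevertheless require double-blind onset, and a parallel run-in table takes the events with run-in onset. The table of reasons for double-blind discontinuation (SAP 10.5.3 and 13.4.3) does not depend on AE onset. The same stop can thus appear in its arm there and be missing from that arm's AE-discontinuation table.
5. **What if it becomes serious?** The general rule in 10.1.2 governs intensity only. The documents do not say which onset date applies when a run-in event later becomes serious. The SAE tables are affected only if the site keeps the run-in date.

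**Size.** The expected number affected in an arm is N × p × q. Here p is the proportion of subjects with an AE ongoing at the first double-blind dose, and q is the proportion of those whose event then worsens. The documents give neither p nor q, so the number cannot be computed. For scale, SAP 4.2 gives 490 randomized: 490 / 6 = 81.7, about 82 per arm, so one subject shifts an arm's incidence by 1 / 82 = 1.2 percentage points.

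**The case against.** The strongest objection is that the start of study treatment in 10.1.2 may mean double-blind start. Protocol 5.2.1 defines treatment-concomitant therapy from the first double-blind dose, and the AE-onset imputation rule in SAP Section 12 moves between double-blind start and study treatment start as if they were one date. Protocol 10.1.1 itself adds that it means the run-in, which suggests that the bare term is not self-evident. On that reading a new AE dated at the worsening is already required, and SAP 5.6.1.1 would count it. The eCRF completion guidelines, which might settle this, are not among the documents. This stands as a real ambiguity. It does not remove the problem: the AE section's own definition favors the run-in reading, and if both readings are open, sites may record the same event differently.

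It is also fair that nothing disappears from the data. The AE listing keeps the event, labelled by period of onset (SAP 10.9.1). Marked laboratory abnormalities, QTcF, hemoglobin and body weight are analyzed by group from measured values. Episodic events that recur after Day 1 have their own onset and are counted; only continuous, unresolved events are exposed.

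A reader might infer a bias of the dose gradient toward zero. The rule applies equally to placebo and lisinopril, so attenuation follows only if worsening is dose-related.

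A reader might also take literally the pointers in SAP 5.6.1.1 to Sections 11.2 and 11.4 for double-blind start and end. Section 11.2 is now run-in start, and 11.4 reads "The randomization date/time is taken from IVRS". The window would then close 30 days after randomization and lose later events. The documents do not support this: the sentence names the double-blind dates, sections with those titles exist (11.5 and 11.6), and other pointers are similarly out of date (SAP 5.2.2 and 5.2.3 cite 11.8 to 11.10 for material now in 11.10 to 11.12). The literal window would also count run-in events as double-blind, the opposite of the point made here. It is a numbering error.

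**Conclusion.** The point holds on the better-supported reading of protocol 10.1.2. Worsening after the first double-blind dose of an event that began in the run-in is absent from the by-arm tables of treatment-emergent AEs, maximum intensity and AEs leading to discontinuation, and the event is counted as run-in without a dose column. On the alternative reading the event would be captured, but inconsistently between sites unless the term is defined.

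The conclusion rests on study treatment including run-in placebo and on the SAP tables being programmed as written. It does not extend to a stated number of subjects, to a demonstrated bias in the dose gradient, or to loss of the event from the listings. The change is worth making because it bears on a dose-selection comparison and costs little.

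**What to change.** - **Protocol 10.1.2 or eCRF guidance:** state that an AE ongoing at the first double-blind dose that worsens afterwards is entered as a new AE with the date of worsening as onset.
- **SAP 5.6.1.1 and 5.6.3:** extend the double-blind definition to onset or worsening from double-blind start onward.
- **If records are already closed** (SAP 4.2 describes a decision taken after database lock): flag AEs with run-in onset that were ongoing at Day 1 and tabulate them by treatment group with worst intensity, seriousness and action taken. Include every AE that led to discontinuation of double-blind treatment in the by-arm discontinuation table, whatever its onset. Because the overwritten record holds only the worst intensity, this table cannot date the worsening and should say so.
- **Numbering:** replace 11.2 and 11.4 by 11.5 and 11.6 in SAP 5.3.1, 5.6.1.1, 5.6.2, 5.6.3, 5.6.7.1 and 5.6.8.1.

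The cost is a completion instruction, a query on AEs ongoing at Day 1, SAP wording and, at most, one extra table. No assessment is added. The downside is slightly more AE records and slightly higher counts of treatment-emergent events.

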10.1.3 Relationship to study treatment

Each AE must be assessed by the investigator as to whether or not there is a reasonable possibility of causal relationship to the study treatment, and reported as either related or unrelated. The determination of the likelihood that the study treatment caused the AE will be provided by an investigator who is a qualified physician.

Essential hypertension Protocol AC-080A201 Version 3 30 May 2016, page 79/112

Confidential

10.1.4 Adverse events associated to study design or protocol-mandated procedures

An AE is defined as related to study design or protocol-mandated procedures if it appears to have a reasonable possibility of a causal relationship to either the study design or to protocol-mandated procedures. Examples include discontinuation of a subject's previous treatment during a washout period leading to exacerbation of underlying disease.

10.1.5 Reporting of adverse events

All AEs occurring after study start (i.e., signing of informed consent) and up to 30 days after DB study treatment discontinuation must be recorded on specific AE pages of the eCRF.

10.1.6 Follow-up of adverse events

Adverse events still ongoing more than 30 days after DB study treatment discontinuation must be followed up until they are no longer considered clinically relevant.

10.2 Serious adverse events

10.2.1 Definitions of serious adverse events

10.2.1.1 Serious adverse events

An SAE is defined by the ICH guidelines as any AE fulfilling at least one of the following criteria:

- Fatal.
- Life-threatening: refers to an event in which the subject was at risk of death at the time of the event. It does not refer to an event that hypothetically might have caused death had it been more severe.
- Requiring inpatient hospitalization, or prolongation of existing hospitalization.
- Resulting in persistent or significant disability or incapacity.
- Congenital anomaly or birth defect.
- Medically significant: refers to important medical events that may not immediately
 result in death, be life-threatening, or require hospitalization but may be considered to
 be SAEs when, based upon appropriate medical judgment, they may jeopardize the
 subject, and may require medical or surgical intervention to prevent one of the
 outcomes listed in the definitions above.

The following reasons for hospitalization are exempted from being reported:

- Hospitalization for cosmetic elective surgery, or social and/or convenience reasons.
- Hospitalization for pre-planned (i.e., planned prior to signing informed consent) surgery or standard monitoring of a pre-existing disease or medical condition that did not worsen, e.g., hospitalization for coronary angiography in a subject with stable angina pectoris.

Essential hypertension Protocol AC-080A201 Version 3 30 May 2016, page 80/112

Confidential

However, complications that occur during hospitalization are AEs or SAEs (for example if a complication prolongs hospitalization).

